Blood culture sampling practices are underpinned by a range of behavioural, cultural and systems factors that may be difficult to address (11). Attitudinal barriers include the importance attached to blood culture diagnostics and views on the utility of blood culture sampling (12, 13). An unpublished systematic review of barriers and enablers to blood culture sampling identified a range of key barriers within the Theoretical Domains Framework domains of: knowledge, behavioural regulation, environmental connect and resources, memory, attention and decision processes, beliefs, and social influence (14). In our recent study involving interviews with acute care clinicians (15), we identified a range of barriers including lack of time and skills, problems of coordination and diffused responsibility, and lack of feedback on the consequences of blood cultures for subsequent patient management.

The purpose of this study is to find out why blood culture sampling is not always successfully undertaken and to increase generalisability of findings through taking a national sample of UK healthcare professionals. Specifically, we set out to assess the behaviours, beliefs and attitudes held by staff who prescribe antibiotics, take blood samples and/or use blood culture test results to inform clinical practice, about blood culture sampling and microbiological testing in acute care. We will also identify predictors of self-reported engagement in timely and appropriate blood culture sampling. This study is part of a wider project that aims to create a bundle of interventions to optimise blood culture sampling practices for acute care patients with suspected severe infection (IRAS 338495 and 332310).

2. Research Questions/Aim

The primary research questions for this study are:

- What are NHS healthcare professionals' attitudes towards blood culture sampling for adult patients with suspected severe infection?
- Do these attitudes differ by professional role and clinical setting? The secondary research questions are:
 - Does our newly developed attitude questionnaire capture key components of the Theory of Planned Behaviour within the context of blood culture sampling?
 - What are predictors of self-reported engagement in clinical activities that form part of the blood culture pathway?

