4.1. Data analysis

Data analysis will involve quantitative methods, including: (1) descriptive statistics of beliefs and perceived barriers to blood culture sampling, rated on likert scales; (2) confirmatory factor analysis to test the hypothesized factor structure of our newly developed questionnaire; (3) Analysis of variance (ANOVA) to test for interactions and effects of professional roles and clinical setting on attitude ratings regarding blood culture sampling; (4) multiple regression analyses to identify predictors or self-reported engagement in the blood culture pathway, and (5) qualitative content analysis of an open-ended question around potential interventions to improve blood culture sampling. The full analysis plan can be found as Appendix B.

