APPENDIX 2 - Analysis plan

1) Have any data been collected for this study already?

No, no data have been collected for this study yet.

2) What's the main question being asked or hypothesis being tested in this study?

Q1. Does our newly developed attitude questionnaire capture key components of the Theory of Planned Behaviour within the context of blood culture sampling?

Q2. What are NHS healthcare professionals' attitudes towards blood culture sampling for adult patients with suspected severe infection? Do these attitudes differ by professional role and clinical setting?

Q3. What are predictors of self-reported engagement in clinical activities that form part of the blood culture pathway?

Q3. What are perceived barriers to healthcare staff engaging in clinical activities related to blood culture sampling for managing suspected severe infection? Do these perceived barriers differ by professional role or clinical setting?

H1. Healthcare staff's attitudes around blood culture sampling will map on to a four-factor structure proposed by the Theory of Planned Behaviour: (1) perceived importance, (2) social norms, (3) self-efficacy and (4) controllability.

H2a. There will be significant differences between the mean ratings of the four attitude dimensions.H2b. Individuals' professional roles and the clinical setting they work in will have a significant effect on their ratings of the four attitude dimensions.

H3. The four attitude dimensions will be significant predictors for self-reported engagement in the requesting of blood cultures, collection of blood culture samples and use of blood culture results.

H4. Perceptions of the most influential barriers to blood culture sampling will differ across professional roles and clinical settings.

3) Describe the key dependent variable(s) specifying how they will be measured.

1. **Attitude variables:** We will assess beliefs and attitudes pertaining to blood culture sampling via 20 authordesigned questions, created to capture different attitude dimensions that are modelled on the Theory of Planned Behaviour. Each attitude question will be measured on a 7-point likert scale ranging from 1 (strongly disagree) to 7 (strongly agree).

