2. Engagement variables: We will assess three single-item, self-reported variables measuring how frequently healthcare staff engage in different aspects of blood culture sampling: (1) requesting samples, (2) collecting samples, and (3) using the results from samples. Variables will be measured on a 5-point likert scale (1= Never, 2 = Hardly any shift, 3 = Some shifts, 4 = Most shifts, 5 = Almost every shift, N/A = this isn't part of my job role).
 3. Barrier variables: We will assess the perceived influences of 29 barriers to blood culture sampling, measured via a 7-point likert scale ranging from 1 (strongly disagree that this factor influences blood culture sampling) to 7 (strongly agree that this factor influences blood culture sampling).

4) How many and which conditions will participants be assigned to?

We will employ a quasi-experimental design, where professional role (doctors vs. advanced clinical practitioners, nurses, paramedics & physician associates vs. healthcare assistants & phlebotomists) and clinical setting (acute medical ward vs. acute surgical ward vs. emergency department vs. critical care unit) will be treated as between-subject IVs.

5) Specify exactly which analyses you will conduct to examine the main question/hypothesis.

H1: We will run a confirmatory factor analysis to test our hypothesized factor structure and validate our attitude questionnaire in the context of blood culture sampling. We will use Maximum Likelihood for our estimation method and assess the goodness of fit of the resulting models using six key statistics: chi-square (χ 2); relative chi-square (CMIN/DF); comparative fit index (CFI); non-normed fit index (NNFI); root mean square error of approximation (RMSEA); and standardized root mean square residual (SRMR). Following identification

Combined Protocol V3.0 22/07/24

of the best model fit, four latent attitude variables will be confirmed, which will be based on the theoretical dimensions of (1) perceived importance, (2) social norms, (3) self-efficacy and (4) controllability in the context of blood culture sampling. For each of these latent variables, factor scores will be calculated by deriving the mean of all constituent variables. We will use these latent variables for our subsequent analyses.

H2a,b: We will run a 3×4 between-within subjects ANOVA to test for interactions and simple main effects of professional role and latent attitude dimension on mean attitude ratings.

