We will run a 4×4 between-within subjects ANOVA to test for interactions and simple main effects of clinical setting and latent attitude dimension on mean attitude ratings.

If significant main effects are detected for either ANOVA, we will conduct Bonferroni-corrected pairwise comparisons as follow-up analyses.

H2: We will run three multiple regression analyses, one for each of our engagement variables. For each regression analysis, predictors will be entered hierarchically in blocks.

Block 1: Demographic variables. This will include *age*, *gender* \rightarrow female/other (1), male (0); and *ethnicity* \rightarrow people of colour (1), white (0). **Block 2: Professional variables**. This will include *professional role* \rightarrow healthcare assistants & phlebotomists (2), advanced clinical practitioners, nurses, paramedics & physician associates (1), doctors (0); *clinical setting* \rightarrow acute surgical ward (3); emergency department (2); critical care unit (1); acute medical ward (0); and *seniority* \rightarrow junior (1), senior (0). **Block 3: Attitudes and beliefs**. This will include the latent attitude variables identified in our factor analysis.

H3: We will produce descriptive statistics for the influence ratings pertaining to each of the 29 barriers to blood culture sampling. We will produce an overall ranking of the 3 most influential barriers and separate rankings of barriers for different professional roles and clinical settings.

6) Describe exactly how outliers will be defined and handled, and your precise rule(s) for excluding observations.

We will exclude participants, who took less than five [revise after piloting] minutes to complete the survey. We will exclude participants, who did not complete all 20 attitude questions.

We will exclude participants suspected of "straight-lining". We will test for this separately across the 20 questions measuring attitudes and 29 questions assessing the influence of key barriers by calculating the standard deviation. Participants will be excluded from analyses if their likert ratings from either section have a standard deviation of \leq 0.45.

7) How many observations will be collected or what will determine sample size?

No need to justify decision, but be precise about exactly how the number will be determined.

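### The survey speaks of effects of professional role and of clinical setting on attitudes, but tests each in a separate ANOVA without the other, so one factor can carry part of the other's effect

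*Protocol*

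**What the plan says.** One of the two primary questions of the survey is "Do these attitudes differ by professional role and clinical setting" (Part 1b protocol, section 2). Appendix 2 (Analysis plan), item 2, turns this into H2b: "Individuals' professional roles and the clinical setting they work in will have a significant effect on their ratings of the four attitude dimensions". Section 4.1 describes ANOVA "to test for interactions and effects of professional roles and clinical setting on attitude ratings". Item 4 of the appendix declares both factors as between-subject variables of one quasi-experimental design.

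Item 5 then fixes two analyses for H2a and H2b:
- for role: "We will run a 3×4 between-within subjects ANOVA to test for interactions and simple main effects of professional role and latent attitude dimension"
- for setting, a 4×4 counterpart that tests interactions and "simple main effects of clinical setting and latent attitude dimension on mean attitude ratings"

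The follow-up is conditional on either of them: "If significant main effects are detected for either ANOVA, we will conduct Bonferroni-corrected pairwise comparisons as follow-up analyses".

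The interactions tested are therefore role by dimension and setting by dimension. No model of the attitude ratings contains role and setting together. They do enter together in Block 2 of the multiple regressions, but the outcomes there are the three engagement variables.

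Section 4.1 refers to the appendix as the full analysis plan, and item 8 of the appendix adds no further analyses. The choice is fixed in this document.

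**The concern.** Respondents come from two staff cohorts, social media and professional networks (section 3.1.2). Sections 3.1.1 to 3.1.3 state no quota or stratification by role or setting, so the role mix within each setting will be whatever the respondents happen to be. If that mix differs and role matters, as H2b predicts, the setting means differ even when setting itself does nothing. The same holds with the factors exchanged.

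The follow-up comparisons inherit the problem, because they stay within each ANOVA. At stake is the interpretation of a primary survey question: whether a difference belongs to the unit, to the profession, or partly to both. The plan separates the two when it models engagement but not when it models attitudes.

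**Working it through.** **The plan's own sample-size figure.** Inputs (Appendix 2, item 7): 4 groups, m = 4 measurements, correlation ρ = .5, f = .25, α = .01, power .80, stated N = 236. For the between factor, λ = N·f²·m / [1 + (m − 1)ρ] = N × .0625 × 4 / 2.5 = 0.1·N, with 3 and N − 4 df. Power .80 needs N = 164 in equal groups. N = 236 gives power .954 and is the N for power .95. The stated power and N do not match, but the error is on the safe side and does not bear on this point.

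**How large the leak can be.** The documents give neither role mix by setting nor a role effect, so both are assumed here. There is no true setting effect in any scenario.

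Worked example:
- Role shares (three role groups) in the four settings: 35/35/30, 45/30/25, 65/30/5 and 20/78/2%.
- Linear role effect with f = .25, so role means are 0, −0.353 and −0.706 SD.
- Setting means are share × role mean, summed: −0.335, −0.283, −0.141, −0.290. Their variance is 0.0053.
- Error variance of the mean of four dimensions at ρ = .5: (1 + 3 × .5)/4 = 0.625.
- Role variance left within settings: .0625 − .0053 = 0.0572.
- Apparent setting effect: f² = 0.0053 / (0.625 + 0.0572) = 0.0078, so f = 0.088.
- With N = 300, λ = 300 × 0.0078 = 2.33. The noncentral F with 3 and 296 df gives rejection in about 22% at .05 and 8% at .01. Simulation gives 20% and 7.7%.

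Simulated rejection of the null hypothesis for setting, N = 300:

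| Assumed mix | Assumed role effect | Setting alone, .05 / .01 | With role in model, .05 / .01 |
|---|---|---|---|
| Equal in all settings | f = .25 | 4.8% / 1.5% | 5.3% / 1.3% |
| Moderately different | f = .25 | 8.5% / 1.6% | 4.0% / 0.9% |
| Strongly different (example above) | f = .25 | 20% / 7.7% | 4.8% / 1.0% |
| 65% doctors in ED, 30–35% elsewhere; single rating | means 0 / 0.4 / 0.8 SD | 24% / 8.7% | 5% / 1% |

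Three milder single-rating scenarios give 6.0%, 9.0% and 11.7% at .05. A larger role effect gives more: with the strongly different mix and f = .40, setting alone is rejected in 45% at .05 and 23% at .01. That is well above the medium effect the plan works with, so I do not rest the point on it.

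**Does the planned sample carry a joint model?** With f = .25, α = .01, ρ = .5 and balanced cells, power .80 for setting needs N of about 161 with role in the model. A role-by-setting term (6 df) needs about 198. At N = 300 power is .989 for setting, .994 for role and .967 for role by setting; at 400 it is .999, above .999 and .996. Unbalanced cells would lower these figures; the cell sizes are not in the documents.

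**The case against.** The best defence is that the primary question asks only whether attitudes differ by role and by setting. That can be read as two marginal questions, and one ANOVA per factor answers them. On that reading the rejections above are not false positives, because the setting means in the simulation really do differ. This stands, and it is why the unadjusted results should be kept. It does not cover H2b or section 4.1, which speak of effects. The word is ordinary ANOVA vocabulary, but readers will take it as attribution.

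The size is also modest in the moderate cases. In the single-rating 24% scenario the leaked effect is f of about 0.09, under 1% of variance, against the f = .25 the study is sized for. Reported with effect sizes it would look small.

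Four stronger readings are tempting and are not supported:
- That role mix does differ between settings, or that EDs have more doctors. No section gives staff mix by setting or by cohort; with an equal mix there is no leak.
- That interventions would be aimed at the wrong target. Nothing makes an ANOVA result choose a target. The Part 1c/2 protocol has co-design workshops drawing on Parts 1a, 1b and 1c together (section 6.2), and what its section 3 names from the survey is potential barriers.
- That section 4.1 contradicts the appendix. It commits to neither a joint model nor a role-by-setting test.
- That sparse role-by-setting cells do not matter in a joint model. An additive model does not need every cell filled, but it needs enough overlap to separate the factors, and it assumes the role difference is the same in every setting.

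**Conclusion.** The point holds as a weakness of model structure. The attitude analysis has no model with both factors, although both are declared in one design, both are said to have an effect, and neither is balanced by recruitment. Part of a role effect can then be reported as a setting effect, or the reverse.

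Whether it will be, and by how much, rests on two quantities the documents do not give. Under the assumptions shown, with N = 300, the setting-only test rejects in about 5% to 24% at .05. At .01, a level the plan states only in its sample-size calculations, the range is about 1% to 9%. The joint model keeps close to nominal throughout. The lower end applies when the mix is equal; the upper end needs a strongly different mix. This is a cheap improvement to a primary survey question, not a flaw that invalidates the planned ANOVAs as description.

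**What to change.** Test H2b in one between-within or mixed model with role, setting, dimension, role by dimension and setting by dimension. Report role adjusted for setting and setting adjusted for role, and base the Bonferroni-corrected comparisons on those adjusted contrasts.

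Keep the unadjusted group means, or the two separate ANOVAs, labelled as description. Tabulate the role-by-setting counts to show that the factors overlap enough to be separated. State that the model assumes additivity, and add a role-by-setting check if cell sizes allow.

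The cost is a change of wording in Appendix 2, item 5, plus a few degrees of freedom: two for role in the setting test, three for setting in the role test. Precision falls slightly where role and setting are strongly associated. No change to recruitment is needed for this.

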3.1. Study Participants

3.1.1. Sample size

The target sample size is 400 healthcare professionals. We considered sample size requirements across a number of different statistical analyses, which we are planning. For our plans to validate a new questionnaire measure, we followed White (2021)'s recommendation to sample 250-350 participants. For our ANOVAs, we ran a G*power calculation for ANOVA (repeated measures, between factors) with 4 groups and 4 measurements, assuming a correlation of up to 0.5. We estimated a power of .80 and an α error probability of .01 to detect a medium effect size f = .25, which returned 236 participants. For our linear multiple regression analysis (fixed model, R2 increase) with 10 predictors, we ran a G*power calculation, estimating a power of .80 and an α error probability of .01 to detect size f = .15, which returned 160 participants. To satisfy sampling requirements for all types of analyses and to account for potential data loss from incomplete submissions and exclusions, we will recruit up to 400 participants.

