We considered sample size requirements across our different analyses. Sample size recommendations for scale validation vary depending on the sample type used. For more specific samples (as opposed to samples drawn from the general population), 250-350 participants have been recommended (White, 2021). For our ANOVAs, we ran a G*power calculation for ANOVA (repeated measures, between factors) with 4 groups and 4 measurements, assuming a correlation of up to 0.5. We estimated a power of .80 and an α error probability of .01 to detect a medium effect size f = .25, which returned 236 participants. For our linear multiple regression analysis (fixed model, R² increase) with 10 predictors, we ran a G*power calculation, estimating a power of .80 and an α error probability of .01 to detect a medium effect size f = .15, which returned 160 participants. To satisfy sampling requirements for all types of analyses and to account for potential data loss from incomplete submissions and exclusions, we will recruit up to 400 participants.

8) Anything else you would like to pre-register?

(e.g., secondary analyses, variables collected for exploratory purposes, unusual analyses planned?) N/A

4. Agency UKHS. English surveillance programme for antimicrobial utilisation and resistance (ESPAUR) report 2020-2021. 2021.

5. Trust N. Antibiotic prescribing: Quality Watch 2024 [Available from:

https://www.nuffieldtrust.org.uk/resource/antibiotic-prescribing#background.

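### Part 1b regressions: clinical setting and professional role are each listed as one integer-coded variable with no indicator coding; for setting, a single slope would have no meaning and could leave the attitude tests under-adjusted

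*Protocol*

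**What the plan says.** All references are to Part 1b of the protocol.

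- **Model.** Appendix 2, item 5: "We will run three multiple regression analyses, one for each of our engagement variables", with predictors entered in three blocks. The paragraph is labelled H2, but its content is the test of H3 in item 2 (attitudes as predictors of engagement).
- **Block 1.** Age, gender (0/1) and ethnicity (0/1).
- **Block 2.** Role is coded "healthcare assistants & phlebotomists (2), advanced clinical practitioners, nurses, paramedics & physician associates (1), doctors (0"), setting is coded "acute surgical ward (3); emergency department (2); critical care unit (1); acute medical ward (0"), and seniority is 0/1. The three-level and four-level variables use the same notation as the binary ones.
- **Block 3.** "This will include the latent attitude variables identified in our factor analysis"; H1 specifies four of these.
- **Power.** Section 3.1.1 has "For our linear multiple regression analysis (fixed model, R2 increase) with 10 predictors". Appendix 2, item 7 repeats this with "estimating a power of .80 and an α error probability of .01 to detect a medium effect size f = .15", "which returned 160 participants".
- **The same variables elsewhere.** Item 4 defines role and setting as between-subject factors. Item 5 analyses them in 3×4 and 4×4 ANOVAs with pairwise comparisons, which assume no order. H2b predicts that attitude ratings depend on role and setting.

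**The concern.** Medical ward, critical care, emergency department (ED) and surgical ward have no natural order. If the 0 to 3 code enters as a number, the model forces the medical-to-critical-care, critical-care-to-ED and ED-to-surgical differences in engagement to be equal. That slope answers no question about settings, and a real difference that does not follow the code order can be missed.

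The second consequence concerns H3. Block 2 is there to remove role and setting differences before the attitudes are tested. A linear code removes only the part of those differences that lies along the code. What is left over can be attributed to attitudes.

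**Working it through.** **1. Does the stated sample size show how the variables enter?**

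Inputs (Appendix 2, item 7): effect size .15, alpha .01, power .80, 10 predictors, N = 160. For an R² increase with *u* tested and *p* total predictors, λ = f²·N, df1 = *u*, df2 = N − *p* − 1, and power is the upper tail of the noncentral F beyond the central critical value.

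- 10 tested of 10: λ = 0.15 × 160 = 24, df2 = 149, power 0.801, so N = 160. The plan's figure is reproduced.
- The effect size must be f² = .15. Read as f, as printed, f² = 0.0225 and N = 998.

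Count of terms:

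- One column each: 3 demographic + role + setting + seniority + 4 attitudes = **10**.
- Indicators: 3 + 2 + 3 + 1 + 4 = **13**. Blocks 2 and 3 alone then hold 2 + 3 + 1 + 4 = **10** tested terms out of 13.
- 10 tested of 13: df2 = 146, power 0.800, so again N = 160.

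Neither the 10 nor the 160 separates the two readings.

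**2. What indicator coding does to the sample size**

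| Tested / total | N for power .80 | Power at 160 | Power at 250 |
|---|---|---|---|
| 10 / 10 | 160 | 0.801 | – |
| 13 / 13 | 176 | 0.735 | 0.961 |
| 4 attitudes / 10 | 119 | 0.934 | – |
| 4 attitudes / 13 | 119 | 0.934 | 0.997 |

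**3. How far a numeric code could distort the attitude test**

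The protocol gives no group means, so every input here is an assumption. The true attitude effect is zero and n = 300.

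*Near worst case.* Four equal settings, engagement means 3.0/3.6/3.6/3.0 in code order, residual SD 1.1, attitude means shifted ±0.4 SD in the same pattern.

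- The code deviations (−1.5, −0.5, 0.5, 1.5) multiplied by the mean deviations (−0.3, 0.3, 0.3, −0.3) sum to 0.45 − 0.15 + 0.15 − 0.45 = 0. The numeric code therefore adjusts for nothing.
- Covariance left between attitude and engagement: 0.4 × 0.3 = 0.12. Attitude variance: 1 + 0.16 = 1.16. Spurious slope: 0.12/1.16 = 0.103.
- Residual variance: (1.21 + 0.09) − 0.12²/1.16 = 1.288. SE = √(1.288/(300 × 1.16)) = 0.0608. Ratio: 0.103/0.0608 = 1.70.
- Rejection at alpha .01: P(Z > 2.576 − 1.70) ≈ 19%. At alpha .05: about 39–40%. Simulation gave 19% and 39%; indicators gave 1% and 5%.

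*Milder patterns, numeric code (simulated):*

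| Pattern | alpha .05 | alpha .01 |
|---|---|---|
| Attitude shift halved to ±0.2 SD | 14–15% | about 5% |
| Only ED differs (attitude +0.4 SD, engagement +0.6) | 10% | 2–3% |
| Both monotone in the code but not linear | 5.2% | 1.0% |
| Attitude linear in the code | 4.2% | 0.7% |

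*Separate simulation.* Unequal group shares, residual SD 1, 3,000 runs, alpha .01:

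| Pattern | Numeric code |
|---|---|
| No group differences | 0.9% |
| Differences linear in the codes | 0.9% |
| Differences in engagement only | 0.8% |
| Critical care and ED 0.5 SD higher in both attitude and engagement | 4.5% |
| Middle role group 0.5 SD higher in both | 3.8% |
| Last two patterns together | 20% |

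Indicators gave 0.8–1.2% throughout.

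**The case against.** The strongest reply is that the plan never says the codes enter as numbers. Each list has a zero level, which is how a codebook marks a reference category, and item 4 treats the same variables as categorical. A reader might infer that the 10 predictors confirm numeric entry. They do not, since 160 is also what 10 tested of 13 returns. That objection stands in full. It does not remove the ambiguity, because item 5 asks for the exact analyses and names neither indicators nor reference levels.

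A reader might also infer that the attitude coefficients are necessarily confounded. The documents do not support that. Bias needs setting (or role) differences off the code line in both attitude and engagement. H2b makes differences in attitude plausible, but nothing shows their shape, or that engagement follows the same pattern. Several of the patterns above leave the error rate at its nominal level, and the 39% and 19% come from means chosen to be orthogonal to the code.

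Two further limits stand. The role codes (doctors; practitioners, nurses and similar; assistants and phlebotomists) follow a rough professional gradient, so a single slope is less arbitrary there. And the regressions answer a secondary question: the primary question, whether attitudes differ by role and setting, is tested by the ANOVAs, which this point does not touch.

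**Conclusion.** The point holds for clinical setting, and more weakly for role. Followed literally, item 5 fits one slope across four unordered settings. That slope cannot be interpreted, and it is inconsistent with the plan's own ANOVA. Numeric entry is the natural reading, not a stated one.

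Under that reading, the type I error of the H3 attitude tests at alpha .01 is about 1% to 19% in the setting-only illustrations, and 20% when role is misfitted too, against about 1% with indicators. These sizes rest on assumed group means and on n = 300, not on anything in the protocol. Sample size is not a reason to keep the single codes: the four-attitude test needs 119 under either coding.

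This should be settled before analysis, but it is a correction to a secondary analysis and does not threaten the survey's main result.

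**What to change.** In Appendix 2, item 5, state that setting enters as three indicators (reference acute medical ward) and role as two (reference doctors), with joint tests on 3 and 2 degrees of freedom.

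In section 3.1.1 and Appendix 2, item 7, give both the tested and the total number of predictors, and write the effect size as f². With 13 model terms, f² = .15, alpha .01 and power .80, N is 176 if all 13 are tested and 119 for the four attitudes.

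The cost is 13 − 10 = 3 degrees of freedom in each model and a few words of text. The target of 400 is unaffected, and item 1 of the plan says that no data have been collected yet.
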